## Randomization

Subjects who have successfully completed the run-in period (intention is to ensure at least 80% adherence to treatment with rivaroxaban placebo bid and aspirin 100 mg od except for extenuating circumstances) and who remain committed to the study as well as those who are being randomized after CABG will be randomized and begin study treatments on Day 1, which will also signal the initiation of the follow-up period. Initially, subjects without a continuous need for treatment with a proton pump inhibitor will be randomized 1:1 to

- pantoprazole 40 mg od or
- matching placebo od,

stratified by center.

All subjects (including those subjects who entered the study while already receiving a proton pump inhibitor) will then be randomized 1:1:1 to anticoagulant therapy stratified by center and by proton pump inhibitor use (randomized to pantoprazole, randomized to pantoprazole placebo, and not randomized, because subject is already taking a proton pump inhibitor) as shown below:

**Group A:** rivaroxaban 2.5 mg bid + aspirin 100 mg od

**Group B:** rivaroxaban 5.0 mg bid + aspirin placebo od

**Group C:** rivaroxaban placebo bid + aspirin 100 mg od

This leads to combinations of randomized study treatment, as displayed in [Table 3-1](#).

 Text modified as per integrated CSP, Version 2.0.

 Text modified as per integrated CSP, Version 2.0.

 Text modified as per integrated CSP, Version 2.0.

 Text modified as per integrated CSP, Version 2.0.

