### 4.2 Handling of Non-compliance to Study Treatment or Follow up

A subject who signed an informed consent form, and, for any reason (e.g., failure to satisfy the in- and exclusion criteria) terminates the study without dispensation of run-in study drug and without run-in exemption for peri-operative CABG, is regarded as a “screening failure”.

A subject who signed an informed consent form and either received run-in study drug or was scheduled for randomization after peri-operative CABG surgery, and, for any reason (e.g., non-compliance during run-in phase or failure to satisfy the in- and exclusion criteria) terminates the study before randomization, is regarded as a “run-in phase failure”.

A randomized subject who permanently stops taking study treatment before their Final rivaroxaban/aspirin Follow-up Visit (for rivaroxaban/aspirin) or their Final pantoprazole/placebo Follow-up Visit (for pantoprazole/placebo) for any reason is defined as having had a premature permanent discontinuation of study treatment (including subjects who were randomized but never started taking any study treatment). The reason for permanent discontinuation of study treatments will be recorded in the CRF. Subjects who continued on rivaroxaban/aspirin study treatment until the global rivaroxaban/aspirin outcomes cut-off date but stopped rivaroxaban/aspirin study treatment before their Final rivaroxaban/aspirin Follow-up Visit will still be considered as study rivaroxaban/aspirin follow-up completers.

However, all subjects will be encouraged to remain on their randomized and pertinent (to the portion of the study) study treatments and under observation until the end of the study. Discontinuation of study treatment is not the equivalent to withdrawal of informed consent. In cases where subjects indicate they do not want to “continue”, investigators must determine whether this refers to discontinuation of study treatment, unwillingness to attend follow-up visits, unwillingness to have

 Text added as per modification 1 in integrated SAP, Version 3.0.

 Text modified as per modification 1 in integrated SAP, Version 4.1.

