For a subject with premature permanent discontinuation of pantoprazole/pantoprazole placebo study medication, the last dose date will be obtained from the Permanent Discontinuation CRF Report. If pantoprazole/pantoprazole placebo study medication was continued until the Final Follow-up Visit, the date of the last dose of pantoprazole / pantoprazole placebo study medication will be the date of the Final Follow-up Visit. If missing or incomplete, the date of last double-blind dose of pantoprazole study treatment is set to the latest logically possible date of pantoprazole study medication administration on or before the earliest of the subject's following dates, the date of last follow-up contact, the date of death, or the common trial close-out date, and no earlier than the randomization date.

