#### 5.1.2 Safety Analysis Set (SAF) - Amended

The safety analysis set for secondary analyses related to the rivaroxaban/aspirin randomization will include all unique randomized subjects who received at least one dose of rivaroxaban/aspirin study medication.

The safety analysis set for secondary analyses related to the pantoprazole randomization will include all unique randomized subjects who received at least one dose of randomized pantoprazole/placebo medication.

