### 6.1.8 Extent of Study Follow-up and Exposure - Amended

The total duration of study follow-up for a subject in the rivaroxaban/aspirin portion of the study and overall will be calculated as follows:

- Total duration of <rivaroxaban/aspirin, study> follow-up =  
Date of last <rivaroxaban/aspirin, study> follow-up contact – Randomization date + 1.

 Text modified as per modification 5 in integrated SAP, Version 3.0.

 Text modified as per modification 1 in integrated SAP, Version 4.1.

Total duration of antithrombotic study treatment will be calculated as follows:

- Total duration of antithrombotic study treatment (including days on/off study drug) =  
Date of last double-blind dose of antithrombotic study treatment –  
Randomization date + 1

For the different types of study medication, total treatment duration will be calculated as:

- Total duration of study treatment <type> (including days on/off study drug) =  
Date of last dose of study treatment <type> – Randomization date + 1,  
where <type> is replaced by rivaroxaban(/rivaroxaban placebo), aspirin(/aspirin placebo),  
and pantoprazole(/pantoprazole placebo).

Descriptive statistics for total duration of study follow-up and study treatment will be provided by treatment group.

Because the number of days off study drug cannot be reliably determined from the CRF data, no study duration excluding study drug interruptions or compliance will be calculated. However, the number and length of study drug interruptions and/or study drug dose reductions as far as documented on any CRF page will be summarized by means of descriptive statistics by randomized study treatments.

Frequency tables will be used to summarize compliance to study drug since last visit (i.e., at least 80% of pills taken) by visit and randomized study treatments.

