### 4.1 Analysis Sets

The following analysis sets will be used for the analysis of the data from CDB2.

- **Intention-to-treat Analysis Set (ITT):**  
The intention-to-treat analysis set, also termed full analysis set in the International Conference on Harmonization (ICH) E9 guideline, includes all subjects randomized to antithrombotic study treatment. The ITT set comprises both subjects randomized to pantoprazole/placebo and subjects not randomized to pantoprazole/placebo.
- **Pantoprazole ITT Analysis Set (pantoprazole ITT):**  
The pantoprazole ITT analysis set comprises all subjects that have been randomized to pantoprazole 40mg or pantoprazole placebo.
- **Pantoprazole Safety Analysis Set (pantoprazole SAF):**  
The safety analysis set for secondary analyses related to the pantoprazole randomization (pantoprazole safety analysis set) will include all subjects randomized to pantoprazole/placebo who received at least one dose of randomized pantoprazole/placebo medication.  
A subject is considered to have taken at least one dose of pantoprazole/placebo study

medication if the date of permanent discontinuation of pantoprazole/placebo study treatment is later than the randomization date.

[figure not shown]

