##### 4.1 Analysis Sets

The following analysis sets will be used for the analysis of the data after full close-out of the COMPASS trial after LTOLE.

- **Intention-to-treat Analysis Set (ITT):**  
The intention-to-treat analysis set, also termed full analysis set in the International Conference on Harmonization (ICH) E9 guideline, includes all subjects randomized to antithrombotic study treatment for the initial study part. The ITT set comprises both subjects randomized to pantoprazole/placebo and subjects not randomized to pantoprazole/placebo.

- Long-Term Open-Label Extension ITT Analysis Set (LTOLE ITT):  
The LTOLE ITT analysis set comprises all subjects who completed LTOLE initiation visit (LTOLE initiation visit date entered).
- Long-Term Open-Label Extension Safety Analysis Set (LTOLE SAF):  
The LTOLE Safety analysis set will include all subjects who completed LTOLE initiation visit and who received at least one dose of LTOLE medication.  
A subject is considered to have taken at least one dose of LTOLE study medication if date of permanent discontinuation of LTOLE study medication is later than the date of the completed LTOLE initiation visit.

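### The date rule that decides who took at least one dose in the pantoprazole and LTOLE safety sets drops subjects who stopped on the first day, and can admit subjects who never started

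*SAP*

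**What the plan says.** Three plans bear on this point: the integrated SAP (version 4.1), the pantoprazole close-out SAP and the LTOLE SAP.

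- **Definition.** Section 5.1.2 of the integrated SAP puts into the pantoprazole safety set those randomized subjects "who received at least one dose of randomized pantoprazole/placebo medication", with no date proxy.
- **Pantoprazole rule.** Section 4.1 of the pantoprazole SAP keeps that definition, then says a subject counts as dosed "if the date of permanent discontinuation of pantoprazole/placebo study treatment is later than the randomization date".
- **LTOLE rule.** Section 4.1 of the LTOLE SAP has the same construction: "if date of permanent discontinuation of LTOLE study medication is later than the date of the completed LTOLE initiation visit".
- **Start of treatment.** In Section 3 of the integrated SAP (Randomization), subjects "will be randomized and begin study treatments on Day 1".
- **Exposure.** Section 6.1.8 of the integrated SAP computes duration for each drug as "Date of last dose of study treatment <type> – Randomization date + 1".
- **Never-starters.** Section 4.2 of the integrated SAP defines premature permanent discontinuation as "including subjects who were randomized but never started taking any study treatment".
- **Missing last-dose dates.** Section 4.5.1 of the integrated SAP has a missing pantoprazole last-dose date "set to the latest logically possible date of pantoprazole study medication administration on or before the earliest of the subject's following dates", namely last follow-up contact, death or trial close-out, and not before randomization.

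**The concern.** Whether a subject was dosed is a fact about drug intake. Neither rule consults a recorded dose; each compares a stop date with the randomization or initiation visit date. Two kinds of subject are at risk of misclassification: the one who was dosed and stopped on the first day, and the one who was never dosed but carries a later stop date.

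The first kind matters more. Someone who stops within hours of a first tablet may well have stopped because of an event, so the exclusion can be related to the outcome that a safety set exists to capture. The loss would fall on the repeat of the GI outcome analysis in the pantoprazole safety set (pantoprazole SAP, Section 5.2.4), on the pantoprazole treatment-emergent adverse event tables (Section 5.4.3), and on the LTOLE adverse event summaries (LTOLE SAP, Section 5.4.3), which name no other population.

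**Working it through.** The plan gives no figure to reproduce. The check applies the rule to the possible cases. Let R be the randomization date (or, for LTOLE, the initiation visit date).

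| Subject | Stop date | Dosed? | Rule as written (after R) | Variant (on or after R) |
|---|---|---|---|---|
| Dosed on day 1, stops that day | R | yes | out: wrong | in: right |
| Dosed, stops on day 2 | R + 1 | yes | in: right | in: right |
| Never dosed, dated at randomization | R | no | out: right | in: wrong |
| Never dosed, dated at a later contact | R + 30 | no | in: wrong | in: wrong |

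**Case 1 against the exposure formula.** With the last dose on R, duration is R − R + 1 = 1 day. The integrated SAP gives this subject one day of treatment; the pantoprazole SAP gives none. The LTOLE SAP has the same conflict: Section 5.1.3 computes time to last dose as the date minus the initiation visit date plus 1, so a last dose on the visit day again gives day 1.

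**Are the stop date and the last-dose date the same thing?** If permanent discontinuation meant the day after the last dose, case 1 would be kept. The text points the other way. Section 4.2.3 of the pantoprazole SAP ends its scope two days after permanent discontinuation and censors two days after the last dose, so it uses the two interchangeably. Section 4.5.1 of the integrated SAP takes the last-dose date of an early stopper from the permanent discontinuation report.

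**Cases 3 and 4.** Section 4.2 of the integrated SAP makes never-starters discontinuations, but nothing says which date they carry. Membership turns on that unstated convention. No comparison of these two dates alone separates case 1 from case 3, because both have a stop date of R.

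**Scale, on assumptions only.** Section 7 of the integrated SAP plans at least 16,440 subjects for the pantoprazole randomization and about 6% early discontinuation in the first six months. The 6% was set for the antithrombotic comparison and is borrowed here.

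- Stops in six months: 0.06 × 16,440 = 986.
- First-day stops if uniform over 182.6 days: 986 / 182.6 = about 5 (0.03%).
- First-day stops if ten times as frequent (assumed): about 54 (0.33%).

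The LTOLE SAP gives no sample size from which a similar range could be formed.

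**The case against.** The strongest reply is that this is a boundary case in secondary tables. Much of that stands.

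- **A reader might infer that the rule does admit never-starters.** The documents do not support that. If never-starters are dated at randomization, the strict inequality excludes them correctly, and it may have been written with that in mind. Only *can admit* is supported; the missing convention is the defect.
- **A reader might infer that first-day reactions in LTOLE go unreported.** They do not vanish. The LTOLE ITT set also carries efficacy outcomes including hospitalization (Sections 5.2.1 and 5.2.2), bleeding (5.4.1), other events of interest (5.4.2) and deaths (5.4.4). Reasons for stopping drug are tabulated (5.1.3), and all data are listed (Section 5). What is lost is the entry in the adverse event summary tables. LTOLE is single-arm with no testing planned.
- **A reader might infer that a pantoprazole result changes.** The GI outcome and its components are tested in the pantoprazole ITT set (pantoprazole SAP, Sections 5.2.3 and 5.2.4), and adverse events are summarized there too (5.4.3). The safety set repeats the former and serves the CSR only for the latter.
- **Person-time from never-starters is negligible.** Even with 0.5% of 16,440 (assumed), 82 subjects at 30 days each add 82 × 30 / 365.25 = 6.7 person-years. Against 16,440 × 3 to 4 years = 49,320 to 65,760, that is about 0.01%.
- **The LTOLE SAP is read with the earlier plans**, so the missing-date imputation is arguably inherited. It is not stated, and the rule there concerns last-dose dates of the randomized phase.
- **The first-dose day in LTOLE is not given**; the Day 1 statement belongs to the randomized phase. A subject whose first dose fell after the initiation visit day is kept. The exclusion bites only on dosing confined to that day.

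None of this removes the contradiction between each set's definition and its date rule.

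**Conclusion.** The point holds in limited form. For both safety sets the wording excludes a subject dosed and stopped on the randomization or initiation visit day, contrary to the at-least-one-dose definition. This rests on reading permanent discontinuation and last dose as the same date, as the pantoprazole SAP does in its own censoring rule. Admission of never-starters is possible, and depends on a date convention that is not stated.

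The number is probably small. The illustration of about 5 to 54 first-day stoppers rests on a borrowed discontinuation rate and an assumed multiplier, and is not an estimate. The reason to act is selectivity and internal contradiction. The consequence is greatest for the LTOLE adverse event tables, where no ITT counterpart is planned; for pantoprazole it is confined to secondary and CSR-only output.

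**What to change.** In Section 4.1 of both the pantoprazole SAP and the LTOLE SAP, replace the date comparison: a subject counts as dosed unless CRF discontinuation, adherence or accountability data show that no study drug was taken.

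If a date rule is preferred:

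1. First exclude documented never-starters, and state what discontinuation date they carry.
2. Then require a last-dose date on or after the randomization date (pantoprazole) or the initiation visit date (LTOLE). Changing the inequality without step 1 is not enough, since it would admit never-starters dated on the first day.
3. State that the missing-date imputation of Section 4.5.1 of the integrated SAP also applies to LTOLE, and apply it before the set is assigned.

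The cost is a few sentences and one changed derivation. Adherence and accountability are scheduled for the randomized phase (integrated SAP, Table 3-2), reasons for discontinuation are recorded (Section 4.2), and LTOLE adherence is collected on CRFs (LTOLE SAP, Section 5.1.3).

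There is a small downside. Section 6.1.8 of the integrated SAP concedes that days off drug cannot be determined reliably from the CRF, so never-starters without documentation would stay in the set. That is in line with the worst-case treatment of uncertain adverse events in Section 6.4.2.1, whose remaining principles both later plans adopt.

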## 4.2 Data scopes and censoring rules

As per study design, in CDB2 the mean follow-up time of subjects not randomized to pantoprazole or pantoprazole placebo is expected to be significantly shorter than the mean follow-up time of those subjects randomized to pantoprazole/placebo. To reflect this difference, subjects randomized to pantoprazole/placebo and the subjects not randomized to pantoprazole/placebo will be displayed separately to avoid confusion, where applicable.

In general, subjects not randomized to pantoprazole/placebo will only be analyzed up until their Final Rivaroxaban/Aspirin Follow-up Visit. I.e., with respect to the pantoprazole randomization analyses will only consider outcomes up until the Final Rivaroxaban/Aspirin Follow-up Visit for those subjects. Analyses of outcomes with respect to antithrombotic randomization will not be repeated for these subjects, because the analysis has been reported in the CSR (PH-39342) / publications of the COMPASS study.

The following data scopes will be applied in the analyses:

1. ITT data scope for CDB2
2. Rivaroxaban/aspirin follow-up data scope
3. Pantoprazole treatment emergent data scope

### 4.2.1 ITT data scope for CDB2

The ITT data scope for CDB2 is the primary data scope for analyses of CDB2 data.

For the ITT data scope for CDB2, only outcome events at or after the date of randomization up until Last Follow-up Date (see Section 6 for definition) will be considered for analysis.

For those subjects with documentation of an outcome event within the ITT data scope for CDB2, time (in days) from randomization to the first occurrence of the event will be derived as:

- o the date of the subject's first event – the randomization date + 1.

This will constitute an uncensored observation.

For those subjects without documentation of an outcome event within the ITT data scope for CDB2, time (in days) from randomization to the censoring date will be derived as:

- the subject's Last Follow-up Date – the randomization date + 1.

This will constitute a right-censored observation.

### 4.2.2 Rivaroxaban/aspirin follow-up data scope

The rivaroxaban/aspirin follow-up data scope includes all outcome events from randomization up until the Final rivaroxaban/aspirin Follow-up Visit, for details please refer to the integrated [SAP](#), version 4.1.

### 4.2.3 Pantoprazole treatment emergent data scope

The pantoprazole treatment emergent data scope includes outcome events from randomization up until two days after permanent discontinuation of pantoprazole study treatment.

It will be used for secondary safety analyses in the pantoprazole safety analysis set. All subjects randomized to pantoprazole/placebo with at least one dose of pantoprazole/placebo study medication and without documentation of an outcome event within the pantoprazole treatment-emergent data scope will be censored at the date of last dose of pantoprazole study treatment + 2 days.

## 5. Statistical Methodology

All data will be listed and all variables will be summarized by means of descriptive statistics according to their type.

Summaries by randomized study treatment pantoprazole and pantoprazole placebo using appropriate descriptive statistics will be provided overall and/or by antithrombotic treatment group for all study variables including demographic and baseline characteristics. The group not randomized to pantoprazole/placebo due to continuous need for a PPI will be presented separately. No imputation will be applied. Descriptive statistics such as mean, standard deviation, median, quartiles, minimum, and maximum will be used to summarize continuous variables. Counts and percentages will be used to summarize categorical variables. Life tables and Kaplan-Meier estimates will be used to summarize time-to-event variables. Graphical data displays may also be used to summarize the data. Confidence intervals will be provided at a 2-sided level of 95% unless otherwise stated.

### 5.1 Population characteristics

The structure of the tables describing population characteristics will closely follow the tables provided for CDB1 but comparing randomized pantoprazole treatment with placebo instead of comparing antithrombotic treatment arms.

#### 5.1.1 Sample sizes

Study sample sizes (PPI related analysis sets) will be tabulated overall and by PPI and antithrombotic treatment arms as follows:

- Study sample sizes by region and country
- Study sample sizes by country and site

### 5.1.2 Subject disposition – Overview/Details at visits

Subject disposition will be presented with primary focus on the PPI related part of the study.

### 5.1.3 Visit and study drug adherence

The following will be tabulated overall and by PPI treatment arm:

- Number of subjects and reasons for premature permanent discontinuation of study pantoprazole medication
- Number of subjects and reasons for premature permanent discontinuation of study rivaroxaban/aspirin medication
- Number of subjects and reasons for premature permanent discontinuation of study follow up, i.e. consent withdrawn or lost to follow-up.

For CSR purposes, incidences for permanent discontinuation of the double-blinded pantoprazole study drug and of the follow-up period will be provided by randomized pantoprazole study treatment groups, based on the case report form data. In addition, incidences for permanent discontinuation of the double-blinded pantoprazole study drug and of the follow-up period will be provided by PPI treatment groups.

Kaplan-Meier estimates will be used to present

- time to the date of last dose of pantoprazole study treatment (calculated as days from randomization), and,
- time to last follow-up date

all calculated as days from randomization, by randomized pantoprazole treatment group.

Other details regarding visit adherence (e.g., visit completed in person, by telephone, through third party) and completion as well as study drug adherence collected via CRFs will be summarized using frequency tables by visit and randomized pantoprazole treatment group.

